#### **4.4 Observation target**

- (1) Demographic data and clinical information: name, age, gender;
- (2) Pathological results of endoscopic tissue biopsy;
- (3) Physical and chemical properties of gastric juice (pH value, absorbance, etc.);
- (4) Diagnostic analysis of extracellular vesicles in gastric juice.

#### **4.5 Determination of Sample Size**

This study is an observational and descriptive one, with no specific sample size requirement. However, based on current domestic and international literature reports, approximately 100 cases are expected to be needed. Meanwhile, adjustments will be made as appropriate considering the situation of patient loss to follow-up and incomplete sample information in our center that cannot be used.

[figure not shown]
#### **4.6 Informed consent situation**

After confirming that the patients meet the inclusion and exclusion criteria, the principal investigator informs all the subjects of the experimental protocol. With the patients' consent, they sign the informed consent form.

#### **4.7 Confidentiality of research information**

The personal information of the subjects will be processed, stored and used in an anonymous manner. The information and data generated during the research process will be properly kept in accordance with the regulations. After the research is completed, the publication of the research results will not disclose the personal information of the subjects.

### **5. Technical route**

## **6. Statistical method**

Statistical software SPSS19.0 was used to analyze the data of this cohort study, and P value < 0.05 was considered statistically significant. For quantitative data, if the data were in accordance with the normal distribution, the mean  $\pm$  standard deviation was used to describe the data. The t test was used for comparison between two groups, and the one-way analysis of variance was used for comparison between multiple groups. If the data did not meet the normal distribution, "median" was used to describe the data, and the differences were compared using the Mann-Whitney rank sum test. For qualitative data, "rate (95%CI)" was used to describe, chi-square test was used to compare the differences between groups, and Logistic regression was used for cross-sectional multivariate analysis of risk factors.

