## 2. Purpose of research

This project aims to study extracellular vesicles in gastric juice under different disease conditions, screen out liquid biopsy markers for the early diagnosis of gastric cancer, and identify biomarkers for disease progression or high-risk populations to achieve early disease prediction, guide endoscopic detailed examination, and reduce missed diagnoses. The research will be conducted at Beijing Friendship Hospital, Capital Medical University. By analyzing the diagnosis and treatment process and gastric juice samples of patients undergoing gastroscopy, the characteristics of extracellular vesicles in gastric cancer patients will be determined, and further guidance for endoscopic detailed examination will be provided. We will conduct the research in accordance with the "Measures for the Ethical Review of Biomedical Research Involving Human Subjects" and the principles of the "Declaration of Helsinki".

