### **4.2. Subjects**

4.2.1 Study population: patients who underwent gastroscopy and treatment in Beijing Friendship Hospital, Capital Medical University from Dec. 2025 to Dec. 2026.

4.2.2 Research Center: Beijing Friendship Hospital Affiliated to Capital Medical University.

4.2.3 Planned enrollment: 100 patients, in which the ratio of gastric cancer and non-cancer patients was 1:1.

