### **4.3 Research process**

1. Patients who met the inclusion criteria were enrolled, and the demographic and medical information of the subjects were collected, including name, gender, age, primary disease, past history, gastroscopic biopsy pathological report, etc.

2. the use of previous studies in gastroscopy drain to collect the clinical routine during the rest of the specimens of gastric juice, extracellular vesicle separation and metabonomics analysis, about 10 to 20 ml/time, according to the result of pathology for specimens of patients with gastric cancer patients and patients with gastric cancer group, the identification of potential biomarkers, diagnosis model is established.

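### Section 6 states one P<0.05 rule with no exception for the vesicle metabolomics screen; read as a per-test rule, it leaves the false share of candidate biomarkers uncontrolled

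*Protocol*

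**What the plan says.** Protocol Section 6 sets a single threshold for the study: software is used "to analyze the data of this cohort study, and P value < 0.05 was considered statistically significant". The tests listed beside it work one variable at a time (t test, one-way analysis of variance, Mann-Whitney, chi-square), followed by logistic regression for risk factors. The section does not name the metabolomics data and does not say whether P is raw or adjusted.

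The marker screen is the purpose of the study. Section 2 sets out to "screen out liquid biopsy markers for the early diagnosis of gastric cancer". Section 4.3 plans "extracellular vesicle separation and metabonomics analysis" on cancer and non-cancer samples, leading to "the identification of potential biomarkers, diagnosis model is established". Section 4.4 lists "Diagnostic analysis of extracellular vesicles in gastric juice" as the fourth observation target, after demographics, pathology, and gastric-juice properties such as pH and absorbance. Section 4.2.3 plans "100 patients, in which the ratio of gastric cancer and non-cancer patients was 1:1". Section 4.5 describes the design in these words: "This study is an observational and descriptive one".

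**The concern.** A 0.05 threshold per test suits a handful of clinical comparisons. In a screen of many features it flags about 5% of those with no true difference. How much of the resulting list is false then depends on how many features truly differ and by how much, and nothing in the rule limits that share.

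This matters because the list is an input to the next step. A diagnosis model built from it could carry false markers, although later multivariable selection may remove some. A reader could judge the false share only if the number of features tested and all P values were reported.

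**Working it through.** **Inputs from the protocol.** Alpha 0.05 (Section 6); 100 patients at 1:1, so 50 v 50 (Section 4.2.3). Section 4.5 gives no effect size, SD or power, so there is no calculation of the plan's own to reproduce.

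**Assumptions, not in the protocol.** Number of features m; proportion truly different, π; standardised difference d; two-sided tests; normally distributed features.

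**Step 1: no feature differs.** Expected false hits are 0.05 × m: 5, 25 or 50 for m = 100, 500 or 1000. With independent features the chance of at least one is 1 − 0.95^m: 0.40 at m = 10 and 0.994 at m = 100. Every hit is false, so the false share is 100%.

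**Step 2: power per feature.** Two-sided t test, 50 v 50, alpha 0.05: 0.318 (d = 0.3), 0.697 (d = 0.5), 0.977 (d = 0.8).

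**Step 3: expected false share among features with P<0.05.**

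False share = 0.05(1 − π) / [0.05(1 − π) + π × power]

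For π = 0.10 and d = 0.5: 0.045 / (0.045 + 0.0697) = 0.392.

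| π | d = 0.3 | d = 0.5 | d = 0.8 |
|---|---|---|---|
| 0.01 | 0.940 | 0.877 | 0.835 |
| 0.05 | 0.749 | 0.577 | 0.493 |
| 0.10 | 0.586 | 0.392 | 0.315 |
| 0.20 | 0.386 | 0.223 | 0.170 |
| 0.50 | 0.136 | 0.067 | 0.049 |

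The share exceeds one half only if π is below 0.05 / (0.05 + power): 13.6%, 6.7% and 4.9% for d = 0.3, 0.5 and 0.8.

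**Step 4: compare with Benjamini-Hochberg (BH).** Simulation of 2000 runs with 1000 features, 100 truly different, 50 v 50. Correlated means correlation 0.5 within blocks of 50 features.

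| Setting | Rule | True hits | False hits | Mean false share |
|---|---|---|---|---|
| d = 0.5, independent | raw P<0.05 | 69.6 | 45.0 | 0.391 |
| | BH q 0.05 | 19.9 | 1.0 | 0.044 |
| | BH q 0.10 | 31.7 | 3.3 | 0.089 |
| d = 0.5, correlated | raw P<0.05 | 69.5 | 45.3 | 0.383 |
| | BH q 0.05 | 20.1 | 1.2 | 0.044 |
| | BH q 0.10 | 31.5 | 3.8 | 0.088 |
| d = 0.8, independent | raw P<0.05 | 97.7 | 45.0 | 0.314 |
| | BH q 0.05 | 85.9 | 4.1 | 0.045 |
| | BH q 0.10 | 91.2 | 9.2 | 0.090 |
| d = 0.8, correlated | raw P<0.05 | 97.7 | 45.4 | 0.308 |
| | BH q 0.05 | 85.7 | 4.4 | 0.047 |
| | BH q 0.10 | 91.2 | 9.6 | 0.091 |

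With 200 features, 20 truly different, the picture is the same: raw mean false share 0.279 to 0.384, BH 0.037 to 0.045 (q 0.05) and 0.077 to 0.090 (q 0.10).

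**Step 5: spread of a single list.** Correlation barely moves the mean but widens the spread. At d = 0.5 with 1000 correlated features, the 95th percentile of the realised false share is 54 to 61% for raw P<0.05, depending on how the true features fall across the correlated blocks. For BH it is about 19% at q 0.05 and 28% at q 0.10. These two also shift with that arrangement.

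**The case against.** The strongest reply is that this is an omission presented as an error. How P values from an omics screen are adjusted is commonly left to an analysis plan, and one may exist that is not shown. Section 6 reads like a generic clinical-data paragraph and contains nothing specific to metabolomics or diagnostic accuracy. An adjusted P below 0.05 would comply with it. Section 5 (technical route) has a heading but no extracted text, and a figure near Section 4.5 is not shown, so the workflow could be described there. Section 4.3 does not say whether the metabolomics is targeted or untargeted, so a large feature count is itself an inference.

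Much of this stands as a limit. A reader might infer that the protocol commits to unadjusted P values for the screen, or that the missing correction is itself the fault; the text supports neither. What remains is that the protocol did fix a threshold, in wording general enough to cover the vesicle data, and named no exception for the one comparison that the rule suits least. That is the natural reading of Section 6, though not a compelled one.

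A second reply is that a descriptive study seeking potential biomarkers may prefer a sensitive first screen. That is fair, and it is why family-wise control is not asked for and the level is left to the sponsor. But the protocol states no confirmation step, and the candidates go on to a diagnosis model.

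**Conclusion.** The point holds as a cheap improvement, with medium confidence. Read as a per-test rule, Section 6 does not control even the expected false share of the candidate list. That conclusion does not depend on the assumed values; its size depends on them entirely. At 50 v 50 the share ranges from about 5% (half the features differ, by 0.8 SD), through 31 to 39% (a tenth differ, by 0.8 or 0.5 SD), up to 100% (none differ).

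A reader might infer that most candidates will be false. The protocol gives no feature count, true proportion or effect size to support that, and the share passes one half only below the break-even proportions shown in the working.

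Nor does BH guarantee a clean list. It controls the expected share, so a single list from correlated features can be appreciably worse than q, though still well below the raw rule in the settings examined.

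**What to change.** In Section 6, confine unadjusted P<0.05 to the few clinical and gastric-juice comparisons (age, gender, pH, absorbance and similar). Then add a sentence to this effect: a vesicle or metabolite feature counts as a candidate biomarker only if its Benjamini-Hochberg q-value, computed across all features tested, is below a level fixed before the data are seen; the number of features tested and all raw P values are also reported. The sponsor sets the level, for example 0.05, or 0.10 given the descriptive aim. If such a rule already stands in another document, Section 6 should cite it instead.

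The change needs no new patients or assays; BH works from the list of P values alone. The real cost is sensitivity to weak markers. With 100 true markers among 1000 features, BH keeps on average about 20 (q 0.05) or 32 (q 0.10) instead of 70 at 0.5 SD, and about 86 or 91 instead of 98 at 0.8 SD. Reporting all raw P values lets readers see the features that fall short.

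### The aim is diagnostic, but Section 6 names no measure of discrimination: quantitative data get group-difference tests at P<0.05, and non-normal data a median without spread

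*Protocol*

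**What the plan says.** Protocol Section 2 gives a diagnostic purpose: vesicle markers that support early diagnosis, direct closer endoscopic inspection and lower the number of missed cancers. Section 4.3 ends with "the identification of potential biomarkers, diagnosis model is established", and Section 4.4 lists "Diagnostic analysis of extracellular vesicles in gastric juice" among the items to be observed. Section 4.2 plans "100 patients, in which the ratio of gastric cancer and non-cancer patients was 1:1".

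Section 6 is the only statistical section. Its relevant content is:

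- Threshold: "P value < 0.05 was considered statistically significant".
- Normal quantitative data: mean with standard deviation. "The t test was used for comparison between two groups", with one-way ANOVA for more than two groups.
- Non-normal quantitative data: the median, with no IQR or range, "was used to describe the data, and the differences were compared using the Mann-Whitney rank sum test".
- Qualitative data: rates with 95% CI and the chi-square test.
- Modelling: "Logistic regression was used for cross-sectional multivariate analysis of risk factors".

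No section mentions ROC or AUC, sensitivity, specificity, a cut-off, or a between-group difference with a confidence interval. The diagnosis model of Section 4.3 has no performance measure attached.

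**The concern.** A test of group difference asks whether two distributions are shifted relative to each other. A diagnostic marker needs something else, namely little overlap between cancer and non-cancer patients. A feature can differ truly between the groups, be tested correctly, and still separate individual patients poorly. This is a separate matter from false positives across many features or from optimism in a fitted model, and neither a multiplicity correction nor validation of the model would supply the missing measure.

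If Section 6 is followed as written, the report on each quantitative feature will be a location summary and a P value. For non-normal features, a bare median in each group leaves the reader unable to judge the overlap. The study could then report significant vesicle features without showing whether any of them would help to reduce missed diagnoses.

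**Working it through.** **The plan's own figure.** The total of 100 cannot be reproduced. Section 4.5 describes the study as one "with no specific sample size requirement" and gives no power, effect size or SD. For orientation only, 50 per group with two-sided 5% significance gives 80% power for a standardised difference d = (1.960 + 0.842) × √(2/50) = 0.56.

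**Inputs.** n1 = n2 = 50 (Section 4.2: 100 patients at 1:1). Significance level 0.05 (Section 6). Assumptions: a two-sided test, which is not stated, and all 100 patients evaluable.

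**Step 1: smallest significant effect.**

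- Mann-Whitney: AUC = U/(n1·n2), with null SE = √[(n1+n2+1)/(12·n1·n2)] = √[101/30,000] = 0.0580. P=0.05 falls at 0.5 + 1.96 × 0.0580 = 0.614.
- t test: d = t(0.975; 98) × √(2/50) = 0.397. Under an equal-variance normal model AUC = Φ(d/√2) = Φ(0.281) = 0.611.

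Both tests put the threshold at an observed AUC of about 0.61.

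**Step 2: what that AUC means for diagnosis (equal-variance normal scores assumed).** For AUC 0.614, d = √2 × Φ⁻¹(0.614) = 0.409.

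| Operating point | Formula | Result |
|---|---|---|
| Sensitivity at 90% specificity | Φ(0.409 − 1.282) | 19% |
| Sensitivity at 80% specificity | Φ(0.409 − 0.842) | 33% |
| Best single cut (sensitivity = specificity) | Φ(0.409/2) | 58% |

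**Step 3: how often a weak but real feature is significant.** Powers are for two-sided 5% tests at 50 v 50. The Mann-Whitney values are simulated with normal data.

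| True AUC | d | Sensitivity at 90% specificity | Power, t test | Power, Mann-Whitney |
|---|---|---|---|---|
| 0.61 | 0.40 | 19% | 51% | 48% |
| 0.64 | 0.50 | 22% | 70% | 68% |
| 0.65 | 0.545 | 23% | 77% | not run |
| 0.654 | 0.56 | 23% | 79% | 78% |

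A real feature that misses about three-quarters of cancers at 90% specificity would therefore usually reach P<0.05.

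**Step 4: what reporting the AUC would show.** Hanley-McNeil SE = √{[A(1−A) + 49(Q1−A²) + 49(Q2−A²)]/2,500}, with Q1 = A/(2−A) and Q2 = 2A²/(1+A).

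- A = 0.61: SE 0.056, 95% CI 0.50 to 0.72.
- A = 0.80: SE 0.045, 95% CI 0.71 to 0.89.

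These intervals distinguish a borderline feature from a useful one. The statement P<0.05 covers both.

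**Sensitivity to evaluable numbers.** Section 4.5 anticipates some unusable samples. If, as an assumption, 40 per group were evaluable, the Mann-Whitney threshold would be 0.5 + 1.96 × √[81/(12·40·40)] = 0.627, so the picture hardly changes.

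**The case against.** **A stronger reading is tempting, and the text does not support it.** A reader might infer that any feature with P<0.05 will be declared a biomarker and entered in the model. No section says so. Section 6 sets a significance convention, and Section 4.3 names an output without an entry rule. What can be said is that no other threshold appears in the document.

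**Group comparison is not all that is planned.** Section 4.3 plans a diagnosis model, Section 4.4 a diagnostic analysis, and Section 6 names logistic regression. This stands, but none of the three carries an accuracy measure, and the regression is tied to risk factors.

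**Spread is not missing everywhere.** Normal data get an SD, from which overlap can be worked out. The gap is confined to non-normal data. The sensitivities in Step 2 rest on normal scores, the case in which spread is reported. For non-normal features the AUC threshold of 0.614 still holds, because it comes from ranks, but the conversion to 19% is only illustrative.

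**Ranking barely changes.** With fixed group sizes, ordering features by Mann-Whitney P or by distance of the AUC from 0.5 gives nearly the same list. The gain lies in showing how large the discrimination is, with its uncertainty. Choosing features one at a time can also drop markers that are useful jointly, which is a reason to report the model's accuracy as well.

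**An analysis plan may add this.** It may, and the exact form of the output could be left to it. But the protocol does state its tests, threshold and summaries, and those do not match the diagnostic aim. A median without spread is a stated choice, not a detail left open.

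**Conclusion.** The point holds in a limited form. Sections 2, 4.3 and 4.4 set a diagnostic aim. Section 6 offers quantitative data only tests of difference, gives non-normal data a median without spread, and attaches no accuracy measure to any feature or model. Following it as written would not answer the diagnostic question.

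At 50 v 50 the only stated threshold is met at an observed AUC of about 0.61, or roughly 19% sensitivity at 90% specificity. A feature with true AUC 0.65 (23% sensitivity at 90% specificity) meets it about 77% of the time by t test. These figures assume a two-sided test and 100 evaluable patients, and the sensitivities and t-test power also assume equal-variance normal scores. It does not follow that the protocol makes P<0.05 its rule for naming a biomarker, because no rule of any kind is written. The change should be made before results are seen.

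**What to change.** In Section 6, state that:

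1. each quantitative vesicle feature, and the diagnosis model, will be reported with AUC and 95% CI, and with sensitivity and 95% CI at one specificity fixed in advance (90%, for example);
2. candidate markers will be judged on these estimates, with the P value secondary;
3. non-normal data will be described by median and IQR.

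The cost is some wording and a little more output. No additional patients, samples or measurements are needed. The drawback for the sponsor is that some statistically significant features will be seen to discriminate poorly.

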## **7. Quality Control**

Formulate research plans to ensure the accuracy, completeness and comprehensiveness of data; record and preserve relevant documents for the purpose of retracing the quality control process; strictly keep patients' information confidential.

